8.1 Definitions

8.1.1. Adverse Event (AE)

An AE is any undesirable event or clinical deterioration that occurs to a study participant during the course of the study; that is, from the time of administration of study drugs until study ends (i.e., until the follow up visit) whether or not that event is considered related to the study drugs, or to a concomitant drug or procedure, e.g.

- any unfavourable and unintended symptom
- physical sign
- abnormal laboratory result
- an illness
- any pre-existing condition that has worsened in grade

Any new clinical sign or clinical deterioration that occurs between signing the consent form and the administration of study drugs is not an AE. This information will be recorded in the medical records, as a pre-existing condition.

Condition associated with severe malaria

Common conditions resulting from a deterioration of severe malaria as per list should not be considered or reported as Adverse Events. They are recorded in the specific section of the CRF.

A list of the most common conditions in severe malaria includes,

- Deterioration of BCS or GCS
- Coma not present at admission
- Convulsions not present at admission
- Posturing not present at admission
- Decompensated shock (children systolic BP <70 mm Hg)
- Compensated shock (capillary refill >3sec /temperature gradient)
- Respiratory distress
- Hypoglycaemia (glucose <3 mmol/L)
- Severe anaemia
- Severe bleeding (requiring blood transfusion)
- Hemoglobinuria
- Severe jaundice
- Renal failure (urine output <0.5 mL/kg/hr >24 hours)

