8. SAFETY REPORTING

This trial will use parenteral artesunate followed by an ACT (expected to be artemether-lumefantrine, or other ACT), drugs that are registered and have been evaluated extensively.

To allow for comparison of safety and tolerability of 1-step injectable artesunate compared to conventional injectable artesunate we will record and review all Adverse Events (AEs) and Serious Adverse Events, (SAEs) that occur in the study.

A symptom questionnaire will be performed daily during hospitalization and at each subsequent visit to the health care facility, to aid in the identification of adverse events.

The investigator is responsible for the detection and documentation of events meeting the criteria and definition of an adverse event (AE), or serious adverse event (SAE), as provided in this protocol.

All SAEs, and AEs will be promptly documented from the moment of randomization in the study to discontinuation of the patient from study participation. Any events occurring between screening and randomization will be considered as baseline, pre-existing conditions. Any conditions that were present at baseline will not be considered adverse events unless the grade of the condition deteriorates.

Each adverse event will be graded according Common Terminology Criteria for Adverse Events (CTCAE) version 5.0:

https://ctep.cancer.gov/protocolDevelopment/electronic_applications/ctc.htm#ctc_50

All adverse events must be recorded in the AE /SAE CRF. To avoid colloquial expressions, the adverse event should be reported in standard medical terminology. Whenever possible, the adverse event should be evaluated and reported as a diagnosis rather than as individual signs or symptoms. If a definitive diagnosis is not possible, then the individual symptoms and signs should be recorded. Whenever possible, the aetiology of the abnormal findings will be documented on the CRF. Any additional relevant laboratory results obtained by the Investigator during the course of this study will be recorded on the CRF.

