8.1.2. Serious Adverse Event

A serious adverse event is an AE that:

- results in death
- is life-threatening i.e. the patient was at risk of death at the time of the AE
- requires inpatient hospitalization or prolongation of existing hospitalization
- results in persistent or significant disability/incapacity
- Any other significant medical condition

More than one of the above criteria can be applicable to the one event. Other significant medical conditions may be considered an SAE when, based upon appropriate medical judgment, they may jeopardize the patient or require medical or surgical intervention to prevent one of the outcomes listed in the definition above.

All AEs must be followed until resolution, or until the AE is deemed permanent or leads to death.

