3.2 Demographics and other baseline characteristics

The following baseline characteristics will be described by study arm in table 1 (below). Variables such as age, heart rate, respiratory rate will be summarized using median and interquartile range. Continuous variables such as weight, height, systolic and diastolic blood pressure, , haemoglobin will be summarized using mean \pm standard deviation. Parasitaemia at baseline will be described as geometric mean and range. Categorical variables such as sex, presence of fever and gametocytaemia at baseline will be summarized using frequencies and percentages.

Table 1. Baseline Characteristics of the Patients

Characteristics	1-STEP AS (N=XXX)	2-STEP AS (N=XXX)	Total (N=XXX)
Age (years), med (IQR)	XX.X (XX.X-XX.X)	XX.X (XX.X-XX.X)	XX.X (XX.X-XX.X)
Male sex, n (%)	XX (XX.X)	XX (XX.X)	XX (XX.X)
Weight (kg), mean (SD)	XX.X (XX.X)	XX.X (XX.X)	XX.X (XX.X)
Height (cm) mean (SD)	XX.X (XX.X)	XX.X (XX.X)	XX.X (XX.X)
Hb (g/dL), mean (SD)	XX.X (XX.X)	XX.X (XX.X)	XX.X (XX.X)
Parasites/ μ L, geometric mean (range)	XX.X (XX.X-XX.X)	XX.X (XX.X-XX.X)	XX.X (XX.X-XX.X)
Impaired consciousness or unrousable coma, n (%)	XX (XX.X)	XX (XX.X)	XX (XX.X)
Prostration, n (%)	XX (XX.X)	XX (XX.X)	XX (XX.X)
Failure to feed and drink without assistance, n (%)	XX (XX.X)	XX (XX.X)	XX (XX.X)
Multiple convulsions, n (%)	XX (XX.X)	XX (XX.X)	XX (XX.X)
Deep breathing, respiratory distress, n (%)	XX (XX.X)	XX (XX.X)	XX (XX.X)
Circulatory collapse or shock, systolic BP < 70 mmHg, n (%)	XX (XX.X)	XX (XX.X)	XX (XX.X)
Clinical jaundice plus evidence of other vital organ dysfunction, n (%)	XX (XX.X)	XX (XX.X)	XX (XX.X)
Haemoglobinuria, n (%)	XX (XX.X)	XX (XX.X)	XX (XX.X)
Suspected pulmonary oedema, n (%)	XX (XX.X)	XX (XX.X)	XX (XX.X)

STATISTICAL ANALYSIS PLAN

Renal failure (< 20 ml urine per hour) , n (%)	XX (XX.X)	XX (XX.X)	XX (XX.X)
Spontaneous bleeding/disseminated intravascular coagulation, n (%)	XX (XX.X)	XX (XX.X)	XX (XX.X)
Several episodes of vomiting in the preceding 24 hrs, n (%)	XX (XX.X)	XX (XX.X)	XX (XX.X)
Severe pallor with respiratory distress OR HCT<15% OR hb<5.0g/dl, n (%)	XX (XX.X)	XX (XX.X)	XX (XX.X)

3.3 Convenience and rapidness of administration of 1-step vs. conventional 2-step parenteral artesunate formulations and Costs of administration of 1-step vs. conventional 2-step parenteral artesunate formulations
Primary objective

To assess:

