3.4 Fever clearance and parasite clearance during treatment, by treatment allocation

Table 4 Clinical recovery*, fever clearance, and parasite clearance by study arm**

	1-STEP AS N=XXX	2-STEP AS N=XXX	Both groups N=XXX	P- value (2-sided)
Hours to fever clearance, mean (SD) (baseline to start of first 24h period <37.5C; temperature was recorded every 4 hours, until day 2, then 6 hourly)				
DRC	XX.X (X.X)	XX.X (X.X)	XX.X (X.X)	X.XXX
Tanzania	XX.X (X.X)	XX.X (X.X)	XX.X (X.X)	X.XXX
All study sites	XX.X (X.X)	XX.X (X.X)	XX.X (X.X)	X.XXX
Day 3 blood smear still positive, n/N (%)** (taking prior clearance or discharge as negative)				
DRC	XX/XXX (XX)	XX/XXX (XX)	XX/XXX (XX)	X.XXX
Tanzania	XX/XXX (XX)	XX/XXX (XX)	XX/XXX (XX)	X.XXX
All study sites	XX/XXX (XX)	XX/XXX (XX)	XX/XXX (XX)	X.XXX
Hours to tolerate oral medication, mean (SD)* (baseline to start of oral ACT)				
DRC	XX/XXX (XX)	XX/XXX (XX)	XX/XXX (XX)	X.XXX
Tanzania	XX/XXX (XX)	XX/XXX (XX)	XX/XXX (XX)	X.XXX
All study sites	XX/XXX (XX)	XX/XXX (XX)	XX/XXX (XX)	X.XXX
Parasite clearance half-life in hours, mean (SD)** (excluding patients with initial count insufficient to estimate half-life)				
DRC	X.X (X.X)	X.X (X.X)	X.X (X.X)	X.XXX
Tanzania	X.X (X.X)	X.X (X.X)	X.X (X.X)	X.XXX
All study sites	X.X (X.X)	X.X (X.X)	X.X (X.X)	X.XXX

*Protocol recommends patients receive a minimum of 3 doses of injectable artesunate before switch to oral ACT. Patients may vary if discharged before 24 hours, died, or referred.

** Parasite dynamics will be affected by patients who are transfused.

STATISTICAL ANALYSIS PLAN
3.5 Safety assessments and tolerability (Incidence of adverse events and serious adverse events by study arms within the first 28 days)

Safety analyses will be based on the whole population that get administered the study drug. That is, the safety and tolerability data will be pooled from all the sites that received the same antimalarial treatment.

The safety and tolerability of 1-STEP AS versus 2-STEP AS will be assessed by comparing the frequency (%) of adverse events and serious adverse events, with particular attention to the variables listed below, which pertain to severe malaria.

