Safety data will be presented in tabular and/or graphical format and summarized descriptively. Any clinically relevant abnormalities or values of potential clinically concern will be described. Patients will be analysed following the intention to treat analysis. All adverse event summaries will refer to treatment emergent adverse events, i.e. adverse events that newly started or increased in intensity after the study drug administration. Adverse events will be graded according to Common Terminology Criteria for Adverse Events (CTCAE). The safety and tolerability summaries will be presented in table 5.

Table 5 Incidence of adverse events within first 28 days by study arm

	1-STEP AS	2-STEP AS	p-value
Number of subjects	XX	XX	
Serious adverse events (SAEs), n/N, (%)	XX	XX	X.XXX
Possible, probable or definite drug related SAEs, n/N, (%)	X/XX (X.X)	X/XX (X.X)	X.XXX
Neurological sequelae at discharge	X/XX (X.X)	X/XX (X.X)	X.XXX
Neurological sequelae at 28	X/XX (X.X)	X/XX (X.X)	X.XXX
Neurological sequelae persisting at end of follow up	X/XX (X.X)	X/XX (X.X)	X.XXX
Grading of adverse events, n/N, (%)	1-2	3-4	1-2
Symptoms			
Impaired consciousness or unrousable coma, n (%)	X/XX (X.X)	X/XX (X.X)	X/XX (X.X)
Prostration, n (%)	X/XX (X.X)	X/XX (X.X)	X/XX (X.X)
Failure to feed and drink without assistance, n (%)			
Multiple convulsions, n (%)			
Deep breathing, respiratory distress, n (%)	X/XX (X.X)	X/XX (X.X)	X/XX (X.X)
Circulatory collapse or shock, systolic BP < 70 mmHg, n (%)	X/XX (X.X)	X/XX (X.X)	X/XX (X.X)
Clinical jaundice plus evidence of other vital organ dysfunction, n (%)	X/XX (X.X)	X/XX (X.X)	X/XX (X.X)
Haemoglobinuria, n (%)	X/XX (X.X)	X/XX (X.X)	X/XX (X.X)
Suspected pulmonary oedema, n (%)	X/XX (X.X)	X/XX (X.X)	X/XX (X.X)

STATISTICAL ANALYSIS PLAN

	X/XX (X.X)	X/XX (X.X)	X/XX (X.X)	X/XX (X.X)	X.XXX
Renal failure (< 20 ml urine per hour) , n (%)	X/XX (X.X)	X/XX (X.X)	X/XX (X.X)	X/XX (X.X)	X.XXX
Spontaneous bleeding/disseminated intravascular coagulation, n (%)	X/XX (X.X)	X/XX (X.X)	X/XX (X.X)	X/XX (X.X)	X.XXX
Several episodes of vomiting in the preceding 24 hrs, n (%)	X/XX (X.X)	X/XX (X.X)	X/XX (X.X)	X/XX (X.X)	X.XXX
Severe pallor with respiratory distress OR HCT<15% OR hb<5.0g/dl, n (%)	X/XX (X.X)	X/XX (X.X)	X/XX (X.X)	X/XX (X.X)	X.XXX
Total	X/XX (X.X)	X/XX (X.X)	X/XX (X.X)	X/XX (X.X)	X.XXX
Laboratory abnormalities					
Creatinine	X/XX (X.X)	X/XX (X.X)	X/XX (X.X)	X/XX (X.X)	X.XXX
Total bilirubin	X/XX (X.X)	X/XX (X.X)	X/XX (X.X)	X/XX (X.X)	X.XXX

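### Nine of 13 symptom rows in the SAP's adverse-event table are conditions protocol 8.1.1 keeps out of AEs when malaria causes them; the SAE rule is unstated and no visible table labels deaths

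*Protocol*

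**What the plan says.** **AE definition.** Protocol 8.1.1 lists 13 common conditions of severe malaria and says: "Common conditions resulting from a deterioration of severe malaria as per list should not be considered or reported as Adverse Events". Their destination is given next: "They are recorded in the specific section of the CRF". The exclusion applies only when the condition results from deterioration of the malaria. Protocol section 8 adds a general baseline rule: "Any conditions that were present at baseline will not be considered adverse events unless the grade of the condition deteriorates".

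**SAE definition.** Protocol 8.1.2 opens with "A serious adverse event is an AE that" and then gives the seriousness criteria. Protocol 8.2, on reporting, treats serious deterioration of severe malaria, death included, as an SAE that is reported monthly and not within 24 hours.

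**SAP tables.** SAP 3.5 compares AE and SAE frequency by arm "with particular attention to the variables listed below, which pertain to severe malaria". It also states: "All adverse event summaries will refer to treatment emergent adverse events", meaning events that start or worsen after study drug. The results go into Table 5, which is titled as an AE incidence table for the first 28 days. It holds SAE rows, neurological sequelae rows, a block of 13 symptom rows and a laboratory block. The symptom rows carry the same wording as the clinical items in the admission table (SAP Table 1).

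**Status of the endpoint.** AE and SAE incidence is exploratory in protocol 5.4.3 and appears among the secondary endpoints in SAP 2.1.3.

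**The concern.** The protocol's definitions and the SAP's main safety table do not fit together. The protocol takes malaria-driven complications out of the AE data; the SAP reports only AEs and then reserves most of its symptom rows for those complications. It does not say whether the dedicated CRF section feeds the rows. Two programmers working from the same documents could therefore produce different tables: one counting every new complication after the first dose, the other counting only the few judged to have another cause.

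The SAE row has a similar problem, and it touches the gravest events. Appendix 4 of the protocol describes mortality as high, with most deaths in the first 24 hours. Protocol 3.2 undertakes to document safety accurately for a formulation not yet deployed in severe malaria. A by-arm count of deaths and new complications is the plainest way to do that, and the visible table shells do not clearly provide it.

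**Working it through.** The plan states no figure of its own on this point. The check is a row count, a comparison of definitions, and one ratio.

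**Step 1. Table 5 symptom rows against the 8.1.1 list** (row names shortened)

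| Table 5 symptom row | Condition in 8.1.1 | Match |
|---|---|---|
| Impaired consciousness or coma | Falling coma score; new coma | close |
| Prostration | none | – |
| Failure to feed | none | – |
| Multiple convulsions | New convulsions | close |
| Respiratory distress | Respiratory distress | close |
| Shock, systolic BP < 70 | Decompensated shock | close |
| Jaundice with organ dysfunction | Severe jaundice | loose |
| Haemoglobinuria | Haemoglobinuria | close |
| Pulmonary oedema | none | – |
| Renal failure | Renal failure (other cut-off) | close |
| Spontaneous bleeding or DIC | Bleeding needing transfusion | loose |
| Vomiting | none | – |
| Severe pallor or anaemia | Severe anaemia | close |

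Close 7 + loose 2 = 9 of 13 (9/13 = 69%); 4 rows have no counterpart. Matching is by condition, not by identical definition.

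**Step 2. Both rules applied literally.** A child develops convulsions after the first dose, judged to be due to worsening malaria. Under 8.1.1 this is not an AE. Under SAP 3.5 the summaries contain AEs only. The event is then absent from the convulsions row. The same convulsions put down to another cause would be counted. The 9 rows are not empty by construction, but what they hold is the complement of what their labels suggest.

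**Step 3. The SAE row.** Under 8.1.2 an SAE must first be an AE, so a listed malaria deterioration cannot be one. Under 8.2, serious malaria deterioration and death from it are SAEs. Table 5 has one row for all SAEs and one for drug-related SAEs, and the SAP does not say which rule applies.

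**Step 4. Deaths.** The visible SAP tables are 1, 2, 4 and 5. None has a row or column labelled as death. The visible Table 5 grade bands are 1–2 and 3–4, while its footnote runs to grade 5, which protocol 8.3.1 defines as death. Death is mentioned only in a footnote to Table 4, as a reason for variation.

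**Step 5. Renal failure.** Table 5 uses less than 20 ml/h; 8.1.1 uses less than 0.5 mL/kg/h for more than 24 hours. The ratio of the hourly cut-offs is 20 / (0.5 × weight in kg):

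- 5 kg (entry minimum): 20/2.5 = 8
- 10 kg: 20/5 = 4
- 20 kg: 20/10 = 2
- 40 kg: 20/20 = 1

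For example, a 10 kg child passing 10 ml/h (1.0 mL/kg/h) meets the Table 5 cut-off and not the one in 8.1.1. Appendix 4 gives 20 ml/h for the adult patient; this trial enrols children under 16. The ratio compares hourly rates alone; the 24-hour condition in 8.1.1 has no counterpart in Table 5.

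**The case against.** The strongest reply is that the SAP's intent is clear enough. It announces attention to variables that pertain to severe malaria, and Table 5 already mixes sequelae and laboratory values under an AE title. On this view the title is loose, the CRF source merely went unstated, and the rows will show malaria complications by arm. That is probably what was meant, and it is why the point is about definitions and table shells. It does not remove the conflict, because the SAP's explicit restriction to treatment-emergent AEs points the other way.

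On SAEs, 8.2 names death from malaria deterioration as an SAE and can fairly be taken as the specific rule. That also stands; what is missing is a statement in the SAP that it governs the table.

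Four stronger readings are tempting and not supported:

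- **That the data will be lost.** Protocol 8.1.1 provides a CRF section, and protocol 5.2 plans follow-up to day 28 to determine final status. The documents show a fault in the table plan, not in collection.
- **That malaria deaths would be kept from the DSMB.** Protocol 8.2 sends all SAEs to the DSMB monthly and classes these deaths as SAEs.
- **That the look-back in the row "Several episodes of vomiting in the preceding 24 hrs, n" proves the block was copied unthinkingly from the admission list.** A symptom questionnaire is taken daily in hospital, and a 24-hour look-back could suit it. The shared wording is a fact; the reason for it is not shown.
- **That listed conditions without a visible row, such as posturing and hypoglycaemia, will go unreported.** SAP 3.5 also undertakes to describe clinically relevant abnormalities. This is generic, but it could cover them.

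**Conclusion.** The concern holds as a conflict of definitions that leaves the main safety table open to more than one reading. Nine of 13 symptom rows are affected; on a literal reading, malaria complications drop out of the by-arm comparison, and on one of two readings so do malaria deaths. The renal definitions contradict each other at every weight except 40 kg on the hourly rate, and in duration at all weights.

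The number of children affected cannot be estimated from the documents. No primary result changes, and protocol 9.2.4 says the study is not designed chiefly for safety. The point is worth fixing because the correction is cheap and the events are the most serious ones in the trial.

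Limits: the CRF and the CONSORT figure are not available, SAP numbering passes from Table 2 to Table 4, and Table 5 is broken in extraction, with an unlabelled line at a page break and an incomplete grade header. The statements on death rows and grade bands therefore cover visible text only. The row count rests on labelled rows, and Table 1 shows the same 13.

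**What to change.** 1. Reconcile protocol 8.1.1, 8.1.2 and 8.2 on whether serious or fatal malaria deterioration is an SAE, and state in SAP 3.5 which rule fills the SAE row.
2. Separate two blocks in Table 5: severe-malaria complications that are new or worse after the first dose, taken from the dedicated CRF section and shown descriptively by arm; and protocol-defined AEs and SAEs. Name the data source of each.
3. Add all-cause deaths by arm to day 28.
4. Reconcile the two renal-failure definitions for events after the first dose.

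The cost is revised table shells and a few sentences in protocol section 8 and SAP 3.5. Someone must check that the CRF section records onset relative to the first dose, and that urine output is recorded if a urine-based renal row stays. If the protocol change counts as substantial, protocol 12.3 requires it to be submitted for approval. No new visits, samples or participants are needed.

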8.1.2. Serious Adverse Event

A serious adverse event is an AE that:

- results in death
- is life-threatening i.e. the patient was at risk of death at the time of the AE
- requires inpatient hospitalization or prolongation of existing hospitalization
- results in persistent or significant disability/incapacity
- Any other significant medical condition

More than one of the above criteria can be applicable to the one event. Other significant medical conditions may be considered an SAE when, based upon appropriate medical judgment, they may jeopardize the patient or require medical or surgical intervention to prevent one of the outcomes listed in the definition above.

All AEs must be followed until resolution, or until the AE is deemed permanent or leads to death.

8.2 Reporting Procedures for Serious Adverse Events (SAEs)/ SUSARs

All SAEs are recorded in a CRF. They need are to be reported as follows:

Safety team:

All SAEs are to be reported to Safety team (PI, Sponsor representative (CTSG), project coordinator, and medical monitor) by e-mail to [contact] within 24 hours of site awareness. If further data is required, additional documentation can be submitted, but an initial report should be submitted within the 24-hour timeframe.

SAE, including death, resulting from a deterioration of severe malaria will not follow expedited reporting (24-hour timeframe), but reported monthly.

DSMB:

All SAEs are reported to DSMB on a monthly basis

Ethics Committee and the Regulatory Authorities:

All SAEs must also be reported to the ECs and the Regulatory Authorities as per required by local guidelines

8.3 Evaluating Adverse Events and Serious Adverse Events

8.3.1. Assessment of Intensity AE or SAE

Each adverse event will be graded according Common Terminology Criteria for Adverse Events (CTCAE) version 5.0. This will be included in the safety monitoring plan.

If an adverse event is not listed in the CTCAE table, the Investigator will assess the severity using the following guidelines:

1 = Mild; asymptomatic or mild symptoms; clinical or diagnostic observations only; intervention not indicated.

2 = Moderate; minimal, local or noninvasive intervention indicated; limiting age appropriate instrumental ADL*

3 = Severe or medically significant but not immediately life-threatening; hospitalization or prolongation of hospitalization indicated; disabling; limiting self-care ADL**

4 = Life-Threatening consequences; urgent intervention indicated

5 = Death related to AE

*Instrumental ADL refer to preparing meals, shopping for groceries or clothes, using the telephone, managing money, etc.

**Self care ADL refer to bathing, dressing and undressing, feeding self, using the toilet, taking medications, and not bedridden. According to age- & culture-appropriateness.

8.3.2. Clarification of the difference in meaning between ‘SEVERE’ and ‘SERIOUS’

The term “severe” is often used to describe the intensity (severity) of a specific event (as in mild, moderate, or severe myocardial infarction); the event itself, however, may be of relatively minor medical significance (such as severe headache). This is not the same as “serious”, which is based on the outcome or criteria defined under the serious adverse event definition and the defined study specific SAEs. An event can be considered serious without being severe if it conforms to the seriousness criteria, similarly severe events that do not conform to the criteria are not necessarily serious. Seriousness (not severity) serves as a guide for defining regulatory reporting obligations.

